6.4. Point of enrolment

A subject is considered enrolled in the investigation when the written informed consent is obtained. The expected duration for each subject is described in section 5.1

6.5. Subject Identification and Confidentiality

Subjects will be identified on the electronic CRF (eCRF), and any other document transmitted to the sponsor by the principal investigator or delegate, by a unique identification number.

Data entered on the eCRF are confidential and will only be available to the sponsor (including sponsor delegates), members of data management teams, the statistician, data monitoring board members or clinical event committee members if involved, members of the EC and if requested to regulatory authorities.

The principal investigator will maintain as part of the investigational file a list identifying all subjects entered into the clinical investigation.

7. Procedures

7.1. Clinical investigation-related procedures

Inclusion Visit (V0), Week 0:

- Introduction to the study and review of Subject information Form
- Informed Consent Form signed
- Inclusion in study and allocation of subject number
- Check of in- and exclusion criteria
- Collect baseline information:
 - Gender (male/female)
 - Age (at time of enrolment (years))
 - Height (cm)
 - Weight (kg)
 - Year of stoma creation (YYYY)
 - Ostomy surgery within 3 months (yes/no)
 - Reason for creation of the stoma (Crohn's disease/ulcerative colitis/Cancer/Other)
 - Stoma Type (ileostomy/colostomy)

- o Temporary/permanent stoma
- Shape of the stoma (round/oval/irregular)
- O Size of the stoma (widest diameter and height of stoma from skin)
- o Information about the current stoma product: Type (1P/2P), Kind (Flat, convex, concave), Brand (Coloplast, ConvaTec, Hollister, Dansac, Salts, other)
- Working status (working, restricted duties, sick leave, unemployed/retired, student)
- Insurance of subjects' wellbeing
- Insurance of subjects' compliance with the CIP

Baseline Visit (V1), Week 0:

- Randomization
- Instruct subject in installation of Heylo™ app (on subjects' own smartphone), if relevant
- Instruct subject in completing todays questionnaires:
 - Emotional Impact (OLI)
 - Coping and in control (OLI)
 - Usual and Social activities (OLI)
 - WHODAS 2.0:
 - Understanding and communicating
 - Getting around
 - Self-care
 - Getting along with people
 - Life activities
 - Participation in society
 - Feeling of security, see section 5.3 and Appendix 4.
- Assessment of:
 - Leakage outside baseplate, see section 5.3 and Appendix 4.
- According to the randomization, instruct subject in use of Heylo™ + Standard of Care or only Standard
 of Care for the next 8 weeks
- Provide Investigational device Heylo™ after measurement of Heylo size, if relevant according to randomization
- Instruct and remind the subject to follow the study specific procedures between visits, and inform subject to complete following questionnaires:
 - o Emotional Impact (OLI) every 2nd week
 - Coping and in control (OLI) every 2nd week
 - Usual and Social activities (OLI) every 2nd week
 - Leakage outside baseplate every 2nd week
 - O WHODAS- every 4th week
 - Understanding and communicating
 - Getting around
 - Self-care
 - Getting along with people
 - Life activities
 - Participation in society
- Review of AEs, ADEs, SAEs, SADEs, Device deficiencies and protocol deviations
- Schedule follow up call 7 days ±2 days after V1 to ensure compliance with the provided investigational device and study procedures and Insurance of subject's wellbeing.
- Schedule visit 2 in 8 weeks ±3 days

Visit 2 (V2), Week 8:

- Insurance of subject's wellbeing and follow-up on subject's compliance with study specific procedures (e.g. completing questionnaires and use of Investigational device + Standard of Care OR Standard of Care only)
- Subject completing todays questionnaires:
 - Emotional Impact (OLI)

- Coping and in control (OLI)
- Usual and Social activities (OLI)
- WHODAS 2.0:
 - Understanding and communicating
 - Getting around
 - Self-care
 - Getting along with people
 - Life activities
 - Participation in society
- Feeling of security, see section 5.3 and Appendix 4
- Assessment of:
 - o Leakage outside baseplate, see section 5.3 and Appendix 4
 - o Change in current stoma product, see section 5.3 and Appendix 4
 - o Change in Heylo size, if relevant, see section 5.3 and Appendix 4
 - o Review of AEs, ADEs, SAEs, SADEs, Device deficiencies and protocol deviations
- Instruct subject in installation of Heylo™ app (on subjects' own smartphone), if relevant
- According to the randomization, instruct subject in use of Heylo™ + Standard of Care or only Standard
 of Care for the next 8 weeks.
- Provide Investigation device Heylo™ after measurement of Heylo size, if relevant according to randomization.
- Instruct and remind the subject to follow the study specific procedures between visits, and inform subject to complete following questionnaires:
 - o Emotional Impact (OLI) every 2nd week
 - Coping and in control (OLI) every 2nd week
 - Usual and Social activities (OLI) every 2nd week
 - o Leakage outside baseplate 2nd week
 - WHODAS- every 4th week:
 - Understanding and communicating
 - Getting around
 - Self-care
 - Getting along with people
 - Life activities
 - Participation in society
- Collect unused Heylo™ devices from subjects who have tested these in the first 8 weeks.
- Collect used Heylo[™] devices (only charger and transmitter), from subjects who have tested these in the first 8 weeks
- Schedule follow up call 7 days ±2 days after V2 to ensure compliance with the provided investigational device and study procedures and Insurance of subject's wellbeing.
- Schedule visit 3 in 8 weeks ±3 days

Visit 3 – Termination Visit (V3), Week 16:

- Insurance of subject's wellbeing and follow-up on subject's compliance with study specific procedures (e.g., completing questionnaires and use of Investigational device + Standard of Care OR Standard of Care only)
- Subject completing todays questionnaires:
 - Emotional Impact (OLI)
 - Coping and in control (OLI)
 - Usual and Social activities (OLI)
 - WHODAS 2.0:
 - Understanding and communicating
 - Getting around
 - Self-care
 - Getting along with people
 - Life activities
 - Participation in society
 - Feeling of security, see section 5.3 and Appendix 4

- Assessment of:
 - Leakage outside baseplate, see section 5.3 and Appendix 4
 - Change in current stoma product, see section 5.3 and Appendix 4
 - o Change in Heylo size, if relevant, see section 5.3 and Appendix 4
 - o Review of AEs, ADEs, SAEs, SADEs, Device deficiencies and protocol deviations
- Collect unused Heylo™ devices from subject who have tested this in the last 8 weeks
- Collect used Heylo[™] devices (only charger and transmitter), from subjects who have tested these in the last 8 weeks
- Termination and completion of the study

Follow-up call - Performed 7 days ±2 days after visit 1 and visit 2:

- Ensure compliance with the provided product and study procedures
- Insurance of subject's wellbeing.

7.2. Flow-chart

Table 4: Chart showing the connection between visits and assessments.

	PERFORMED BY	INCLUSION VISIT	BASELINE VISIT	TEST VISIT	TEST VISIT AND TERMINA- TION VISIT	FOLLOW-UP CALL
VISIT	(e)	VO	V1	V2	V3/TERMI- NATION VISIT	7 DAYS ±2 AF- TER VISIT 1 AND VISIT 2
WEEK	4	WEEK 0	WEEK 0	WEEK 8	WEEK 16	WEEK 1 AND WEEK 9
VISIT WINDOW	-	¥.	2	±3 DAYS	±3 DAYS	± . €0
GENERAL						
Review of Subject information	Investigator	Х				
Signed informed consent Form	Investigator	х				
Inclusion and allocation of sub- ject number	Investigator	х				U.
Check of in- and exclusion crite- ria	Investigator	х				
Collect Baseline information	Investigator	Х				
Insurance of subjects' wellbeing	Investigator	х	х	Х	×	Х
Insurance of subjects' compliance with the CIP	Investigator	Х	Х	х	х	Х
Randomization	Investigator		×			
Instruction in installation of Heylo™ app and instruction in ac- cess to link with questionnaires	Investigator/Subject		×	×		
QUESTIONNAIRS						
Emotional Impact (OLI)	Subject		х	×	X	
Coping and in control (OLI)	Subject		Х	×	Х	
Usual and Social activities (OLI)	Subject		X	×	х	
WHODAS 2.0	Subject		X	×	×	
Feeling of security	Subject		Х	×	Х	
Leakage outside baseplate	Subject		х	х	X	
Change in current stoma product	Investigator			Х	х	
Change in Heylo size	Investigator			х	×	
Remind subject to complete questionnaires between visits	Investigator		Х	х		
PROCEDURES	15.5					
Instruction in use of Heylo and SoC, according to IFU (if relevant according to randomization)	Investigator		×	x		
Measure size and provide Heylo (according to Randomization)	Investigator		Х	х		
Collect unused Heylo devices (if relevant) and used charger and transmitter	Investigator			х	х	
Schedule follow up call 7 days ±2 days after visit 1 and visit 2	Investigator		Х	Х		
Schedule next visit	Investigator		Х	Х		
Assess AEs/ADEs/SAEs/SADEs, Device Deficiencies and protocol deviations	Investigator		х	х	х	х
Complete eCRF	Investigator	X	×	X	Х	X

7.3. Case Report Forms

All assessments and observations throughout the investigation must be carefully recorded in an electronic CRF (eCRF). Details about data capture can be found in section 11.1

7.4. Supplementary materials and equipment (if applicable)

Sponsor will provide the PI, or delegate with supplementary materials for this investigation. Supplementary materials would be:

Computer with access to CRFs

8. Risk - benefit analysis and ethical considerations

8.1. Risk-benefit analysis of the investigational device

A risk analysis according to ISO 14971 Application of risk management to medical devices has been conducted. Risks have been proven minimized or eliminated through appropriate design control, confirmed by pre-clinical bench, laboratory, and clinical testing.

All unacceptable risks related to the device have been mitigated as far as possible and have been deemed acceptable for the clinical study. The Heylo™ device is already CE marked.

8.2. Risk-benefit for subjects participating in the clinical investigation

The investigation is conducted in accordance with current law and applicable standards, see section 15. Statement of Compliance. The rights, safety and well-being of human subjects shall prevail over the interest of science of society.

Risks in this investigation are considered to be equal to the use of ostomy products already on the market. Risks associated with the use of ostomy products are skin irritation and mechanical trauma. Please also see Adverse events, adverse device effects and device deficiencies section 18.

There is no known interaction between the use of the investigational device and the medication participants can take. Disadvantages of testing (trial engagement) may be the time spent on visits and responding to questions regarding product change.

Possible benefits for the subjects in this investigation, are that subjects are notified if a leakage occur, which maybe will be beneficial for the subjects in regard to the quality of life and maybe minimize the worry about leakage.

8.3. Risk Analysis for the conduct of the clinical investigation

A risk assessment of the clinical investigation will be conducted initially prior to the first subject enrolment and periodically re-assessed based on any new risks identified through the process. This assessment will be completed throughout the duration of the investigation, as defined by the study team. A risk-based monitoring strategy may be implemented including on-site remote, and central monitoring. Details of the strategy are defined in the monitoring plan.

8.4. Delegation of responsibility

Before initiation of the clinical investigation, sponsor must be provided with Clinical investigation personnel signed and dated curriculum vitae (not more than 2 years old) to verify their qualifications. Clinical investigation personnel are those, who treat or evaluate subject data in the clinical investigation. Also, the sponsor will ensure that all Clinical investigation personnel are trained in the investigation procedures, how to complete the eCRFs, procedure for reporting an adverse event or serious adverse event (how, when, to whom), and who to contact in case of emergency related to the investigational device.

9. Monitoring Plan

The sponsor is responsible for ensuring appropriate monitoring of the clinical investigation activities as described below.

The monitor will be the primary contact for the PI and the study nurses.

Monitoring activities are mandatory as per good clinical practice, however the extend and depth of these activities depend on the criticality of the clinical investigation, speed of enrolment, the experience of the Clinical investigation personnel in carrying out clinical investigations and specific study designs.

For the purpose of this clinical investigation the below described monitoring procedures have been determined.

9.1.1. Site selection visit

Depending on the prospective clinical investigation sites experience with the specific investigational device, an onsite qualification or site selection visit shall be performed during which the feasibility of the clinical investigation requirements will be discussed and common agreement between sponsor and principal investigator shall be reached. This visit may also be replaced by one or more phone calls if the principal investigator is known to the sponsor.

9.1.2. Initiation visit

An initiation visit with full training on all aspects of the clinical investigation will be provided. The initiation visit will be held as a physical meeting or remotely using Microsoft Teams, Skype or Face time and the visit will be held as close to study start as possible.

9.1.3. Monitoring visits

The sponsor shall determine the extent and nature of monitoring appropriate for the clinical investigation based on the risk assessment. The sponsor shall ensure, through oversight of the clinical investigation and timely adverse event reporting, that unanticipated adverse device effects are identified and investigated rapidly so that, where necessary, additional risk control measures can be implemented.

The dedicated monitor is to ensure adherence to the clinical investigation plan, the safety of the subjects, accurate data recording on the e-CRFs and to monitor recruitment rates and adherence to follow-up schedules. During the clinical investigation, monitors shall check that appropriate written informed consents have been obtained. The principal investigator shall permit and assist the monitor to carry out verification of completed e-CRFs against data in the source documents.

The principal investigator can delegate tasks to his collaborators, however the roles and responsibilities as time period of involvement for each clinical investigation personnel must be documented on the Site Personnel signature and Delegation list as well as training received before getting involved with the clinical investigation must be documented in the Clinical Investigation Training Log.

The monitor shall inform the sponsor about any problems relating to facilities, technical equipment, or medical staff involved in the clinical investigation. The monitor shall also be responsible for notifying such deficiencies in writing to the principal investigator and convene with the clinical investigation personnel appropriate and timely corrective actions.

The sponsor, or delegate, will provide clinical monitoring, including review of eCRF with verification to the source documentation, as defined below.

The monitor shall make written reports to the sponsor, including documentation of any deviations after each visit and provide written follow up action items if any, to the principal investigator and/or clinical investigation personnel.

All data collected can be directly entered in the eCRF and the Smart Trial system will by edit checks ensure that all fields are completed in the eCRF. Monitor will ensure by 100% monitoring, that all queries are timely resolved.

Source data verification will be performed to the extent it is possible. The Source Data Specification Form must be completed at the initiation visit detailing the location of the source data for each data point. Where no source data (besides the eCRF) is available the contents of the eCRF will be monitored.

The informed Consent Form and AE/ADE will be 100% monitored for timely completeness.

Only the investigator, delegated clinical investigation personnel and the sponsor representatives will have access to all the eCRF's.

9.2. Source data verification

Source data is all information in original records, certified copies of original records of clinical findings, observations, or other activities in the clinical investigation, necessary for the reconstruction and evaluation of the clinical investigation. This includes source data initially recorded in an electronic format.

All documents and data related to the clinical investigation handled by clinical investigation personnel, shall be produced, and maintained in a way that assures reliability, integrity, control, and traceability, and shall be appropriately stored to provide a complete history.

The Principal Investigator shall assure the accuracy, attribution, completeness, legibility, and timeliness of the data reported to the sponsor in the eCRFs and in all required reports. All printed copies of electronic source documents shall be certified, as indicated by a dated signature by the clinical investigational personnel at the time the document is printed. Special requirements should be applied to the capture, review, and retention of electronic source data, to ensure reliability, quality, integrity, and traceability.

The data reported in the eCRFs shall be derived from source documents and be consistent with these source documents, and any discrepancies shall be explained in writing. The eCRF can serve as the source document and this must be documented on the Source Data Specification Form. The Source Data Specification Form must be completed at the initiation visit detailing the location of the source data for each data point agreed upon by the Principal investigator.

10. Statistical considerations

10.1. Statistical design, method, and analytical procedures

The primary objective will be evaluated by analysing the primary endpoint whereas the secondary objective will be evaluated by analysing the secondary endpoint. The analyses of the exploratory endpoints will be used to further evaluate and explore the primary and secondary objectives.

All baseline measurements, endpoints and assessments will be summarized by descriptive statistics and/or listed. Endpoints and assessments will be summarized by product and time for evaluation, if relevant. Descriptive statistics for continuous variables are presented with N, Mean, SD (standard deviation), Median, Min and Max, where N denotes the number of subjects contributing with non-missing data. For discrete variables, descriptive statistics are presented with N and percentage, where percentage is based on the total number of subjects/observations with non-missing data.

All statistical analyses are made with SAS version 9.4 (SAS Institute Inc., Cary, NC)

10.1.1. Definition of analysis populations

Intention to Treat (ITT) and Safety populations will be defined at a formal data review meeting before database lock. As a minimum, the data manager, the clinical manager, and the statistician will be involved in the classification of subjects.

The ITT population (full analysis set) will be constituted by all randomised subjects with valid informed consent who have been exposed to at least one product, with information on at least one endpoint.

The Safety population will constitute by subjects who have given informed consent.

All statistical analysis will be based upon the ITT population whereas adverse events and device deficiencies will be assessed based on the safety population. Invalid individual data points may be omitted from analysis even though the corresponding subject is part of the ITT population. Any exclusion of data points will be documented.

A formal per protocol (PP) population is not planned due to the explorative nature of the investigation. Considering the data obtained it might be considered to make additional explorative analyses based on a subset of the ITT population.

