5.7. Randomization procedure

All subjects that meet the inclusion and exclusion criteria will be randomized into one of two treatment sequences at V1, with a cross-over after 8 weeks (Visit 2). Subjects with stoma surgery less than 3 months, will be stratified according to time since surgery.

Treatment sequences:

Sequence A: Heylo™ + Standard of Care cross-over to Standard of Care

Sequence B: Standard of Care cross-over to Heylo™ + Standard of Care

When testing the Heylo™ it must be done together with subject's usual ostomy product and in the Standard of Care period subjects will only use their own product.

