10.2. Sample size

The Emotional impact score (scale from 0-100) will be measured every 2nd week and all measurements will be part of the primary analysis whereas the primary comparison will be evaluated at the end of each test period.

The sample size calculation is based on a simplified model (paired 2-sided t-test). The result of the analysis will be adjusted for multiple testing and therefore a test level of 0.025 will be applied in the sample size calculation. Based on data from the previous CP308 investigation (PP population), it is assumed that the total standard deviation of the primary endpoint is 20.6 and that the total variation 20.6² is divided so that the residual variation is 14.4².

Based on the above assumptions 108 subjects should answer the questionnaires at the end of each test period to ensure a power of 81%, if the true difference between the two treatments (with and without HeyloTM) is 6 (minimal important difference is in the range of 5-10 according to the validation of the OLI score) [7]. To take a potential drop-out (25%) into account it is recommended to include 144 subjects.

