If any deviations to the investigation plan are detected during the monitoring visit, the Monitor shall ensure the site reports all deviations in the eCRF or on the Deviation log in the Investigator File. Additionally, the monitor must report any deviation noted during the visit in the Periodic Monitoring Report.

Monitor will align with data management in each investigation, how data management will be informed about all deviations.

The following information about the deviation will be collected:

- Date the deviation took place.
- State what the deviation is related to.
- Does the deviation affect data integrity?
- Does the deviation affect the subject's safety?
- Clear and concise description of the event.
- Corrective action taken.

14. Device Accountability

All access to the investigational devices (Heylo $^{\text{M}}$) used in the clinical investigation is controlled by storage procedures and device accountability logs as described below. The investigational devices must only be used in this clinical investigation and only according to the CIP.

Sponsor keeps a device accountability log that states the physical location of all investigational devices.

The PI or an authorized designee keeps records documenting the receipt, use and return and disposal of the investigational devices, which includes:

- Date of receipt.
- Identification of each investigational device (batch no./serial no./unique code).
- The expire date, if applicable.
- The date(s) of use.
- Subject identification.
- The date on which the investigational device was returned/explanted from the subject, if applicable.
- The date of return unused, expired or malfunctioning investigational devices, if applicable.

15. Statement of compliance

The clinical investigation is conducted in accordance with:

- Ethical principles that have their origin in the Declaration of Helsinki, 1964, Last amended at the 59th WMA General Assembly, Brazil, October 2013.
- MDD 93/42/EEC as amended by Directive 2007/47/EC (commonly known as the Medical Device Directive).
- MDR (EU) 2017/745
- ISO 14155:2020 "Clinical Investigation of medical devices for human subjects Good clinical practices".
- Any applicable regional or national regulations will be specified in the country specific CIP.

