18.3. Device deficiency

A device deficiency is the inadequacy of the investigational medical device or comparator with respect to its identity, quality, durability, reliability, usability, safety, or performance. This includes malfunctions, use errors and inadequacy in the information supplied by the manufacturer including labelling.

Example: Transmitter not able to charge.

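### Does a Safety population defined by consent alone dilute the by-product adverse-event and device-deficiency rates?

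*Combined protocol and SAP*

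**What the plan says.** Section 10.1.1 defines two sets. The ITT set requires randomisation, exposure to at least one product and data on at least one endpoint. The other set requires only consent: "The Safety population will constitute by subjects who have given informed consent". The same section says that "adverse events and device deficiencies will be assessed based on the safety population".

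Section 10.1 gives the general rules for tables. "Endpoints and assessments will be summarized by product and time for evaluation, if relevant", and for discrete variables the "percentage is based on the total number of subjects/observations with non-missing data". Section 5.3 places adverse events and device deficiencies under its Assessments heading, so these rules can be read to cover them.

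In section 5.7, Sequence A starts with Heylo and the other arm is the reverse: "Sequence B: Standard of Care cross-over to Heylo™ + Standard of Care". Sections 5.1 and 5.7 both say that Heylo is worn with the subject's own ostomy product, which is also the comparator. Section 18.3 covers both: "A device deficiency is the inadequacy of the investigational medical device or comparator".

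Section 10.2 supplies the only drop-out figure: "To take a potential drop-out (25%) into account it is recommended to include 144 subjects".

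**The concern.** The ITT definition has an exposure condition and the safety definition, placed next to it, has none. Consent is given at V0, randomisation follows at V1, and the second product starts only at V2. A Sequence B subject who leaves before V2 never wears Heylo, and a Sequence A subject who leaves before V2 has no Standard-of-Care-only period. Section 6.3 says withdrawn subjects are not replaced. Some consented subjects may also never be randomised.

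If every by-product percentage were divided by the full consented set, people who could not have had an event under a product would count as event-free under it. Rates would be too low, and if the two sequences lost different numbers before V2, the ratio between products would shift as well. No sentence states the event denominator by product, or the period to which an event belongs. What would be at stake is the summary safety tables in the report.

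**Working it through.** **Inputs.** 108 completers, 25% drop-out and 144 subjects (section 10.2); two sequences (section 5.7), taken as 72 each; an illustrative true rate of 10%, the ceiling of the under-10% figure for peristomal skin irritation in Table 5 (section 18.2). Drop-out timing and its split by sequence are not in the documents and are assumed.

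**Plan's own figure.** 108 / (1 − 0.25) = 144, which reproduces. Potential drop-outs: 144 × 0.25 = 36.

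**Reading 1: subjects reviewed under the product.** Table 4 (section 7.2) schedules an event review, with eCRF completion, at V1, V2, V3 and the follow-up calls. Section 9.1.3 says edit checks ensure that all eCRF fields are completed. Under section 5.1 an early leaver has a termination visit. A subject who leaves before V2 therefore has event data for the first product and none for the second. With percentages by product on non-missing data, that subject drops out of the second product's denominator. The factor is 1 and a true 10% is reported as 10%.

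**Reading 2: the whole consented set, all 144 randomised.** Heylo factor = (144 − Sequence B losses before V2) / 144. Standard-of-Care-only factor = (144 − Sequence A losses before V2) / 144.

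| Losses before V2 | A | B | Heylo factor | SoC-only factor | 10% shown as (Heylo; SoC-only) | Ratio multiplied by |
|---|---|---|---|---|---|---|
| 18, even | 9 | 9 | 135/144 = 0.9375 | 0.9375 | 9.4%; 9.4% | 1.00 |
| 36, even | 18 | 18 | 126/144 = 0.875 | 0.875 | 8.75%; 8.75% | 1.00 |
| 18, split 1:2 | 6 | 12 | 132/144 = 0.917 | 138/144 = 0.958 | 9.17%; 9.58% | 132/138 = 0.957 |
| 36, split 1:2 | 12 | 24 | 120/144 = 0.833 | 132/144 = 0.917 | 8.33%; 9.17% | 120/132 = 0.909 |
| 36, all in A | 36 | 0 | 144/144 = 1 | 108/144 = 0.75 | 10%; 7.5% | 144/108 = 1.33 |

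Reversing the 1:2 splits gives 1.045 and 1.10. The last row shows that the two products need not both be diluted.

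**Consented but never randomised.** The number is not given. If it were 10% or 20% of those consented (160 or 180 people), the even-split factors would be 135/160 = 0.84 or 135/180 = 0.75 with half the losses before V2, and 126/160 = 0.79 or 126/180 = 0.70 with all of them. The share should be small, because criteria are gone through by phone before consent (Table 3, section 6.2). Table 4 shows no event review at V0, so under Reading 1 these people have no event data and do not enter.

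**Precision.** The 95% half-width at 10% is 1.96 × √(0.1 × 0.9 / 135) = 5.1 points, or 5.2 points with 126. The even-split shifts are 10 − 9.375 = 0.6 and 10 − 8.75 = 1.25 points. At the 1% ceiling for allergic irritation in Table 5 they are 0.06 to 0.13 points.

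**Comparator deficiencies.** The subject's own product is worn in both periods, so a randomised subject who leaves before V2 has still used it. Drop-out does not dilute deficiency rates for the comparator under either reading. Reading 2 affects only Heylo events and adverse events in the Standard-of-Care-only period.

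**The case for a change.** The strongest case for a change is that the plan never says what non-missing means for an event. A blank questionnaire is plainly missing, but an event that did not happen may leave no entry, so two analysts could follow the text and report different rates. An adverse device effect is by definition tied to use of Heylo, and a subject who never wore it is not at risk. A reader may also set the observed rate beside the under-10% figure in Table 5. Under Reading 2 a true rate of up to 10/0.9375 = 10.7% or 10/0.875 = 11.4% would appear below 10%. The trial is open-label and analysed by the sponsor.

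It stands that the denominator and the assignment to period are not written down. The event forms are not reproduced, so the documents cannot show whether a review without findings is recorded as such, or whether an onset date is collected. The rest carries less weight. Scheduled reviews by visit make subjects reviewed under the product the natural meaning. V2 separates the two periods, and section 7.1 lists the event review there ahead of instruction in the next product, so most events fall clearly on one side. For Heylo, section 14 adds that "The PI or an authorized designee keeps records documenting the receipt, use and return and disposal of the investigational devices", with dates of use by subject. Populations are settled at a review meeting before database lock, and the statistician is blinded until lock (section 5.8). Table 5 lists expected incidence and is not a test limit. An explicit rule could also mislead: counting each deficiency under the product period in use would book a fault in the subject's own baseplate to the Heylo period.

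**Conclusion.** The definition is by consent alone, and the by-product event denominator is not spelled out. The dilution does not follow from the plan as written. Sections 5.3, 7.2, 9.1.3 and 10.1 together lead to a denominator of subjects with event data under each product, and a factor of 1. The consent-based set does its own job, which is to keep every reported event in view.

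If an analyst did divide by the whole set, the understatement would be 0.6 to 1.25 points at a true 10%, against an interval of about ±5 points. This assumes that all consented subjects are randomised and that losses fall evenly on the sequences, with half or all of the 36 before V2. One-sided losses or many unrandomised subjects would enlarge it, to 2.5 points for one product or 3 points for both in the extreme cases worked above. Those cases again need the less natural reading. Comparator deficiencies would be untouched by drop-out.

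No safety hypothesis is planned, the pass/fail criterion in section 10.4 uses only the primary and secondary endpoints, and the reporting in sections 18.7 and 18.8 is event by event. An analyst would settle the denominator when laying out the safety tables, so no change to the plan follows.
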